8.3 Measures

Adherence (Primary Outcome). For each participant, adherence will be calculated based on the overall proportion of adherent days (defined dichotomously based on whether a patient took all prescribed doses for the day within 2 hours of recommended time). Participants who are 95% adherent or above will be classified as adherent (1) and those below will be considered not adherence (0). For therapies that have more than one dose per day, we will also calculate the proportion of doses taken among all prescribed doses. Additionally, we will evaluate persistence as a secondary adherence outcome (defined as the number of consecutive days on the regimen and conversely gaps in overall treatment) to assess how Penny may impact different dimensions of adherence. Adherence will also be assessed via self-report (using a validated visual analog rating scale)^{34,35} and prescription refill orders from the EMR to assess accuracy of self-report and provide contingency measures to support potential, yet unlikely, failures in MEMS caps.³⁶

Exploratory Outcomes. Across the intervention study, we will quantitatively assess patient-reported outcomes at various time-points to reduce burden and capture longitudinal changes. Specifically, we will measure medication beliefs and practices³⁹, health-related quality of life (HRQOL),³⁷ symptom burden,^{38,39} patient satisfaction,⁴⁰ financial toxicity,⁴¹ social and behavioral determinants of health (SBDH),⁴² medication self-efficacy,⁴⁷ patient-provider communication, and health literacy.⁴⁰ HRQOL will be measured using the EuroQol EQ-5D, a 5-item index that assesses mobility, self-care, pain, usual activities, and anxiety/depression, and provides a composite score of general HRQOL.³⁷ Symptom Burden will be measured using the Edmonton Symptom Assessment Scale (ESAS).^{42, 43} Patient Satisfaction will be measured by a single item measuring overall patient satisfaction from FACIT-TS-PS, a validated survey.⁴⁰ Financial Toxicity will be measured using the 11-item Comprehensive Score for financial Toxicity (COST) instrument, developed to assess financial toxicity in patients with cancer.⁴¹ SBDH will be assessed by a validated panel of measures recommended by the Institute of Medicine.⁴² Medication self-efficacy will be measured by the 13-item Self-Efficacy for Appropriate Medication Use Scale (SEAMS), which has been validated for this purpose.^{43,44} Patients in the intervention arm will also assess usability using the Health Information Technology Usability Evaluation Scale (Health-ITUES). Lastly, we will capture impact of COVID on patient experiences and care. Clinical characteristics (tumor and treatment specifics), acute care utilization (emergency room and hospital admission), and mortality will be measured as count variables across the study period using EMR data and also patient self-report to capture any visits outside our healthcare system. Prior to study launch, we pilot tested the survey measures to assess participant burden and reduced. All final survey items are included in the Appendices.

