1. PROTOCOL SUMMARY

Title	Implementation Strategies for Monitoring Adherence in Real Time (iSMART)
Short Title	iSMART Trial
Co-Principal Investigators	[name], MSW, MPH [name], MSHP
Co-Investigators	[name] [name] E. [name] [name], MSCE
Design	Prospective, randomized controlled trial
Objectives	
 • Aim 1: To test the effects of a mobile phone-based chatbot (“Penny”) to improve adherence to oral targeted therapies in approximately 170 patients with non-small cell lung cancer. • Aim 2: To use mixed methods approaches with 30 clinicians and 30 patients to explore factors shaping the acceptability, effectiveness, and future implementation of Penny into routine cancer care.
Trial Duration	Estimated 12 months (December 2020-November 2021)
Study Sites	The University of Pennsylvania Health System
Sample Size	Estimated 170 patients and 30 clinicians
Patient Trial Eligibility	
 • Adult patient (age > 18 years) with advanced NSCLC at recruiting site at UPHS who is receiving one of the following oral therapies: afatinib, erlotinib, dacomitinib, gefitinib, osimertinib, alectinib, brigatinib, crizotinib, or lorlatinib • Patient possession of a mobile device that can send/receive SMS texts • Ability to respond to questions and engage with “Penny” in English • Ability to provide informed consent to participate in the study • Blanket approval from the patient’s medical oncologist to be approached
Interventions	
 • Treatment Arm: Patients in the treatment arm will receive access to the mobile phone-based intervention (“Penny”). Penny is a conversational agent (“chatbot”) that engages patients in real time via text messaging, allowing for bidirectional communication between clinicians and patients, longitudinal symptom monitoring with self-management support, and motivational cues to promote adherence. The chatbot will remind patients how and when to take their oral targeted therapies (based on prescribed regimen) and provide self-management and monitoring of mild side effects guided by clinical pathways. • Usual Care: Patients in the usual care arm will receive standard of care for symptom monitoring and management of side effects, which includes patient education at the time of prescribing and direction to call providers or triage nurses if anything arises between appointments.

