4.2 Primary Outcome

The primary outcome is adherence to prescribed oral targeted therapy across the 12-week trial period. Adherence is defined by the overall proportion of adherent days and classified dichotomously as adherent if total proportion of days is $\geq 95\%$. Longitudinal adherence outcomes for all participants will be captured using microelectronic monitoring system (MEMS) caps, surveys, and electronic medical record (EMR) data.

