6. RANDOMIZATION

6.1 Groups

Arm 1: Intervention Group

The intervention is an automated, text-messaging program (chatbot) named “Penny” that is guided by artificial intelligence and natural language process. Penny engages patients in real time via text messaging and continues to learn from interactions. Patients can also directly communicate with Penny at any time. Core functionalities include: (1) real-time dosing instructions, (2) motivational reminders, and (3) symptom monitoring with self-management support. Penny transmits data from text interactions into the secure online dashboard in real time, allowing for enhanced communication and longitudinal monitoring between clinicians and patients. Penny is essentially a virtual care team member, always available to support patients receiving complex oral anticancer therapies. Preliminary data from 10 cancer patients indicate that Penny helped patients to manage side effects and adherence, and can be integrated into care safely and effectively.²⁸ This project will expand upon these findings to evaluate the efficacy of Penny as a patient-directed intervention, and to explore how multilevel mechanisms may impact its acceptability and effectiveness in routine care.

Over an approximate 12-week treatment period, Penny will guide patients randomized to the treatment arm through when and how to take their oral therapies. Penny will additionally monitor patient-reported side effects based on the PRO version of Common Terminology Criteria for Adverse Events (PRO-CTCAE) grading and established clinical pathways used currently at Abramson Cancer Center to escalate and manage patient-reported symptoms (See Appendices).^{29,30} If the side effect is determined to be Grade 1-2 (mild to moderate), patients will be walked through self-care by the chatbot utilizing clinically approved and pre-determined symptom management pathways. If the side effect is deemed Grade 3 (severe) or higher or if the chatbot does not recognize the symptom to triage, the patient will be advised to call his/her care team and a real-time escalation message will be sent to the clinical

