research team's inbox to follow-up directly with the patient. While the chatbot will be responding independently based on embedded algorithms, clinical research team members will monitor and audit conversations daily between the patient and Penny to validate its safety, track for any information that may be relayed to the patient incorrectly and intervene upon these events to guarantee patient safety. Clinical research team members include [name] (Physician, Medical Oncology), [name] (Nurse Practitioner, Medical Oncology), [name] (Clinical Pharmacy Specialist, Thoracic Oncology), and [name] (Outpatient Clinical Oncology Pharmacy Specialist). Additionally, any Grade 3-4 toxicities or side effects that are severe will be triaged directly to the patient's care team. Coding corrections that are not related to symptom monitoring (e.g. inability to recognize new words or commands from patients) will also be reviewed in real-time within the chatbot by Memora Health team members to improve the quality of communication. All issues will be tracked and any adverse events or deviations from protocol will be reported to the IRB as outlined below. To provide additional safety, the research team will communicate clearly (in writing and verbally at several time points) that the intervention is experimental, and that patients should always reach out to their care team directly if they are uncertain or if they are facing an emergency.

Arm 2: Usual Care

Patients in the usual care arm will receive standard of care for symptom monitoring and management of side effects for patients with cancer at Abramson Cancer Center. This includes patient education at the time of prescribing and guidance to call providers or triage nurses if anything issues or questions arises between scheduled appointments.

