8.2 Assessment Procedures

MEMS Caps. Adherence data will be assessed via MEMS caps, which capture a date and time stamp each time the pill bottle is opened. MEMS caps are considered the gold standard of objective adherence measurement over other methods of adherence monitoring,^{31,32} and have been used successfully in previous studies of oral anticancer agents.^{5,25} MEMS data will be scanned to a secure web portal by research staff at the time of clinic appointments. All participants will receive MEMS cap(s) regardless of study assignment. Participants will be instructed to use this system for storage throughout the study, and to log any bottle openings for purposes other than pill ingestion (e.g., to check remaining supply) in a daily journal. After patients complete the baseline survey, a study team member will mail the MEMS Caps directly to the patients with instructions on how to install the MEMS cap. Patients will be contacted by phone approximately 7-10 days after the MEMS cap is mailed to them to confirm receipt and answer any questions. Patients will be instructed to begin using the MEMS cap the day immediately following the phone call as this will be their study start date.

Online Surveys. Trial participants (Aim 1) will be asked to complete online surveys at three timepoints: baseline assessment (T0) will occur at time of enrollment, followed by mid-point assessment approximately 6 weeks later (T1), and final assessment occurring within 2 weeks of trial completion (T2). Data will be captured via REDCap, a secure, web-based application for collecting and managing survey data³³. For REDCap data, patients will receive individualized links to each survey and will be contacted up to three times by email, text message, and/or phone to complete each survey. To increase data completion and study retention incremental compensation will be provided to patients. Specific measures to be assessed in the survey are described below.

Medical Record Data: Medical record data from enrolled patients will be abstracted across the study period to evaluate diagnostic and treatment changes, clinical characteristics, and healthcare utilization. We will also use medical record data to identify and recruit potentially eligible patients as outline in the HIPAA waiver.

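### The primary outcome scores each dose against a reference time that the plan does not define or make common to both arms, while the intervention itself prompts when to dose

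*Combined protocol and SAP*

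**What the plan says.** Section 8.3 (Measures) defines an adherent day as one on which the patient "took all prescribed doses for the day within 2 hours of recommended time". A patient is classed as adherent if at least 95% of days qualify, and section 4.2 states the outcome as "adherence to prescribed oral targeted therapy across the 12-week trial period".

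The text available does not define the recommended time. It does not say who sets it, when it is fixed, or whether one rule applies to both arms.

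The measuring device is the same for everyone. Section 8.2 says "All participants will receive MEMS cap(s) regardless of study assignment", and the caps "capture a date and time stamp each time the pill bottle is opened". They supply the opening time but not the time against which it is judged.

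Instruction on timing differs by arm. Section 6.1 says "Penny will guide patients randomized to the treatment arm through when and how to take their oral therapies", and the Protocol Summary ties the reminders to the prescribed regimen. For usual care, section 6.1 says "This includes patient education at the time of prescribing and guidance to call providers or triage nurses".

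The sensitivity analyses in section 9.1 move only the percentage cut-off (80%, 90%, 100%). Section 8.3 adds a proportion of doses taken for drugs given more than once a day, persistence, and self-report and refill orders as accuracy and contingency measures.

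**The concern.** The primary outcome depends on a clock time, and the only dose-time prompting described during the trial is the intervention. That raises two separate questions.

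- **Is the yardstick the same in both arms?** If Penny's message time were used as the reference for Penny patients and some nominal time for usual care, the prompted arm would be judged against its own prompt. A difference could then appear with no change in behaviour.
- **What does a positive result mean?** Even with one common reference, Penny could raise the proportion classed as adherent by moving the same doses closer to a set time. That is a different finding from more doses being taken. Every cut-off in the planned sensitivity analyses keeps the 2-hour window, so none of them separates the two.

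**Working it through.** **1. The plan's own power figure.** Inputs from section 5.5: 170 enrolled, 15% loss, 72 per arm, 65.5% adherence in controls, a difference of 20.9 points, Fisher's exact test. Loss: 170 × 0.85 = 144.5, or about 72 per arm. Intervention rate: 65.5 + 20.9 = 86.4%. Exact enumeration of the two-sided test at 0.05 (level and sidedness assumed, since the power statement gives neither) yields 80.03%. The stated 80% is reproduced and is not in dispute.

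**2. How tight the rule is.** Twelve weeks is 84 days. 0.95 × 84 = 79.8, so 80 adherent days are needed and 4 failures are allowed. With five off-window days, 79/84 = 94.0%, and the patient is non-adherent even if every dose was taken.

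**3. Effect of the reference on a patient who takes every daily dose.** Let δ be the distance in hours between the patient's habitual time and the reference, and σ the day-to-day SD of dose time. The chance that a day falls in the window is

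q = Φ((2 − δ)/σ) − Φ((−2 − δ)/σ),

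and the chance of being classed adherent is P(X ≥ 80) with X ~ Binomial(84, q). The values of δ and σ are assumptions.

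| δ (h) | σ (h) | q | P(adherent) |
|---|---|---|---|
| 0 | 0.75 | 0.992 | above 99.9% |
| 0 | 1 | 0.954 | 66.4% |
| 1 | 0.5 | 0.977 | 95.7% |
| 1 | 0.75 | 0.909 | 10.9% |

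A patient with σ = 0.75 h goes from almost certainly adherent to about one chance in nine when the reference moves by one hour.

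**4. Gap between arms with no true effect.** Both arms take doses identically: the daily probability of taking has mean 96.5% and varies between patients by a beta distribution with intraclass correlation 0.1, so that about 79% reach 95% of 84 days when timing is ignored. There are 60,000 simulated patients. A day counts if the dose is taken and falls in the window. Penny patients are given δ = 0. Usual-care patients have δ drawn from a normal distribution with the SD shown. All these inputs are assumed.

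| SD of usual-care offset (h) | Adherent, σ = 0.5 h | Gap (points) | Adherent, σ = 0.75 h | Gap (points) |
|---|---|---|---|---|
| 0 (same as Penny) | 79% | 0 | 76% | 0 |
| 0.25 | 78% | 0 | 73% | 2 |
| 0.5 | 76% | 3 | 62% | 13 |
| 1 | 58% | 21 | 40% | 36 |

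Gaps were taken before rounding.

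**5. What such a gap would do to the test.** Suppose 65.5% in each arm would be adherent without the window, and a share f of those in usual care fail on timing alone. The gap is 65.5 × f points. Rejection probabilities are for the two-sided Fisher test at 72 per arm.

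| f | Gap (points) | Probability of rejection |
|---|---|---|
| 0 | 0 | 3.3% |
| 5% | 3.3 | 4.7% |
| 10% | 6.6 | 9.4% |
| 20% | 13.1 | 30.2% |
| 30% | 19.7 | 61.3% |

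The documents give no value for f, and do not say whether the 65.5% rate was itself measured with a 2-hour window.

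**The case against.** A reader might infer that the rule as written biases the comparison toward Penny. The documents do not support that. The rule refers to a recommended time and does not mention Penny's message. The same time stamps judged against one reference score the same in either arm, so prompting alone cannot cause differential scoring. The Protocol Summary links the reminders to the prescribed regimen, which could supply one common reference.

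Nor can one say that usual care has no recorded dosing time. Those patients receive education at prescribing, both arms get a phone call before the study start date (section 8.2), and the survey items sit in appendices whose content is not in the available text. The primary statistician and analyst are blinded (section 6.3), which makes arm-specific scoring less likely without excluding it.

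It can also be argued that timing is part of adherence as section 8.3 defines it, and that dosing instructions in real time are a core Penny function. Better timing would then be a genuine effect on the defined outcome. This is right as far as it goes: under a common reference the issue is one of interpretation and not of measurement bias.

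Finally, the plan has measures with no stated window. They give partial cover. The doses-taken proportion is limited to drugs given more than once a day, persistence measures something else, and self-report and refill orders are accuracy checks and contingencies. For once-daily drugs no window-free MEMS adherence proportion is planned.

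These points remove the claim of demonstrated bias. They leave the undefined reference and the missing analysis.

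**Conclusion.** The concern holds in conditional form. The reference time in the primary outcome is undefined and is not shown to be common to both arms, in a trial whose intervention acts on dose timing. Arm-dependent scoring is neither stated nor ruled out.

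The size depends on facts that the plan does not give. With a common reference and identical behaviour the spurious gap is 0. If the usual-care reference alone is misplaced, the illustrative gap is about 0–2 points at an offset SD of 0.25 h, 3–13 at 0.5 h and 21–36 at 1 h, beside a design difference of 20.9 points. These figures rest on assumed offsets, assumed timing SDs and a zero offset for Penny. They show sensitivity and are not estimates of bias in this trial.

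The narrowness of the rule (five off-window days in 84) and the absence of a window-free MEMS proportion for once-daily drugs do not depend on those assumptions. The matter should be settled before the data are scored, because it affects what a positive result can be said to show.

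**What to change.** 1. Define the reference time in section 8.3. Record each patient's own usual or planned dosing time in the baseline survey, which is completed before randomisation (sections 6.2 and 7.2), and use it to score both arms. Do not update it from later survey answers or from Penny's prompts: the T1 survey falls about six weeks in, when a Penny patient's planned time may already be the prompted one. Change it only when the prescribed regimen changes, by the same rule in both arms. This fixes a scoring reference and sets no clinical dosing time.
2. In section 9.1, name as a key sensitivity analysis the same ≥95% rule applied to MEMS days on which all prescribed doses were taken at any time that day. Reported beside the primary result, it separates a timing effect from a change in doses taken.

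If a common reference is already in use, one sentence saying so settles the question of equal scoring; item 2 is still needed.

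The cost is one baseline survey item and one extra model run. MEMS opening times are already collected in both arms.

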5.4 Target Population

Aim 1. The study aims to enroll 170 adult patients (18 years or older) with advanced NSCLC who have initiated oral targeted therapies at UPHS. These include afatinib, erlotinib, dacomitinib, gefitinib and osimertinib for patients harboring sensitizing EGFR mutations; and alectinib, brigatinib,, crizotinib, and lorlatinib for patients with anaplastic lymphoma kinase (ALK) or ROS1 rearrangements. To be eligible, participants must be receiving ongoing cancer care at a participating site; have access to a mobile phone with SMS text messaging capabilities; be able to read and respond to questions in English; and must have started taking oral targeted therapies no earlier than January 1, 2020 and no later than the end of study recruitment (estimated October 2021).

Aim 2. The study aims to interview 30-45 patients and 15-30 clinicians. Patients will be eligible if they are enrolled in the intervention trial (Aim 1). Clinicians will be eligible if they actively provide care for cancer patients on targeted oral therapies at one of the study sites (including but not limited to oncologists, advanced practice providers, triage nurses, and pharmacists).

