6.2 Assignment

Participants will be randomized individually to 1 of the 2 arms using REDCap randomization module, stratified by three conditions: 1) medication status (new or prevalent starts), 2) drug class (ALK vs ROS1), and 3) study hospital (PCAM vs PPMC). Enrolled patients will learn their assignment (open label) following completion of the baseline survey.

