9. ANALYSIS PLAN

9.1 Primary Analyses

Our primary analyses will use an intent-to-treat (ITT) approach using repeated measures logistic regression to compare the overall effect of the intervention on patient adherence. We will also explore potential differences in secondary outcomes across arms. Baseline clinical and survey data will be used

to assess potential differences in treatment groups (i.e., socio-demographics and clinical risk factors) using parametric or nonparametric tests as appropriate. Data quality, normality, and other assumptions will be assessed prior to analysis. Using repeated measures logistic regression fitted using generalized estimating equations (GEE), we will compare the proportion of adherent days between Penny and usual care. Data will be treated as binary outcome (0/1) over the study period. Models will contain a predictor term for treatment arm, will be adjusted for time (discrete week), and will contain subject specific random effects and fixed effects for site. Patients will be categorized as adherent (outcome=1) across the study period if the total percentage of adherent days is $\geq 95\%$ similar to previous studies⁷; other percentages (80%, 90%, 100%) will be explored in sensitivity analyses. Persistence will be treated as repeated measure survival data and will be summarized as median survival time using Kaplan-Meier methods. We will also generate summary statistics (including mean adherence rate) to help describe the study population and inform the design of further studies.

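### The all-doses-on-time rule makes the 95% test harder for patients on more than one dose a day, and dosing frequency is left to chance: neither stratified nor in the primary model

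*Combined protocol and SAP*

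**What the plan says.** Section 8.3 (Measures) defines an adherent day by "whether a patient took all prescribed doses for the day within 2 hours of recommended time", and a patient is classed as adherent when at least 95% of days qualify. The same paragraph recognises regimens with several daily doses: "For therapies that have more than one dose per day, we will also calculate the proportion of doses taken among all prescribed doses". That extra measure is given no timing window, no threshold and no place in the primary analysis.

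Section 6.2 stratifies randomisation by medication status, drug class (ALK vs ROS1) and hospital. Section 9.1 sets out the primary model: "Models will contain a predictor term for treatment arm, will be adjusted for time (discrete week), and will contain subject specific random effects", plus fixed effects for site. Doses per day appear in neither list. Drug class is not in the model. As its levels are written it does not cover "afatinib, erlotinib, dacomitinib, gefitinib and osimertinib for patients harboring sensitizing EGFR mutations", which 5.4 makes eligible. Section 9.2 allows exploratory interaction tests on clinical characteristics and other factors, without naming dosing frequency.

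**The concern.** The day fails if any one dose is missed or late. A patient with two doses a day has two chances to fail it, against the same 95% cut-off. Dosing frequency is therefore a predictor of the primary outcome that follows from the definition itself, unless doses on one day always stand or fall together.

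It is also available before randomisation. Section 7.2 lists drug type and prescription among the data used to program Penny, and MEMS records cannot be scored in either arm without knowing how many doses were due. With about 72 evaluable patients per arm, the arms can differ by chance in the share on multi-dose regimens. That would shift the primary comparison with no pre-specified way to account for it, and a choice to adjust made after seeing the imbalance would be open to criticism.

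**Working it through.** **Inputs from the protocol.** 12 weeks (4.2), so 84 days at full follow-up. Section 5.3 ends observation earlier if therapy stops, so 84 is the maximum. Cut-off 95% (8.3): 0.95 × 84 = 79.8, so at least 80 adherent days. Control rate 65.5%, detectable difference 20.9 points (86.4% with Penny), 72 per arm, Fisher's exact test, 80% power (5.5).

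**Inputs assumed.** Two-sided alpha 0.05. Two doses a day as the multi-dose case. The multi-dose share, per-dose on-time probability *p*, within-day correlation ρ and between-patient spread are not in the documents, so ranges are shown.

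**Step 1, the plan's own figure.** Exact power of Fisher's test, 65.5% vs 86.4%, 72 vs 72: 80.0%. It reproduces.

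**Step 2, the rule at equal per-dose behaviour.** P(pass) = P(X ≥ 80), X ~ Binomial(84, q), with q = p once daily and q = p² twice daily (independent doses).

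| p | once daily | twice daily | twice daily, if 95% of 168 doses were required |
|---|---|---|---|
| 0.96 | 75.4% | 20.3% | 76.8% |
| 0.97 | 89.2% | 44.2% | 93.2% |
| 0.98 | 97.3% | 76.0% | 99.3% |
| 0.99 | 99.8% | 97.4% | 100% |

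The last column shows that the gap comes from the all-doses day rule.

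**Step 3, anchored at the planned control rate.** Set once-daily patients to pass at 65.5%. Use q = p² + ρp(1 − p), and let *p* vary between patients as logit-normal with SD 0, 1 or 2. With SD 0, p = 0.954 and p² = 0.910.

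| SD between patients | ρ = 0 | ρ = 0.5 | ρ = 1 |
|---|---|---|---|
| 0 | 11.6% | 31.6% | 65.5% |
| 1 | 40.5% | 51.1% | 65.5% |
| 2 | 52.2% | 57.9% | 65.5% |

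**Step 4, effect of a 10-point imbalance in twice-daily share.** Shift = 0.10 × (65.5% − twice-daily rate).
- SD 0, ρ = 0: 0.10 × 53.9 = 5.4 points.
- SD 0, ρ = 0.5: 0.10 × 33.9 = 3.4 points.
- SD 1 to 2, ρ = 0: 0.10 × 25.0 = 2.5 down to 0.10 × 13.3 = 1.3 points.
- SD 1 to 2, ρ = 0.5: 0.10 × 14.4 = 1.4 down to 0.10 × 7.6 = 0.8 points.

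**Step 5, how likely such an imbalance is.** SD of the difference in share = √(2f(1 − f)/72). For f = 10% this is 0.050, a 95% range of ±9.8 points. For f = 30% it is 0.076, or ±15.0 points.

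**Step 6, power.** Under the extreme model (SD 0, ρ = 0), twice-daily patients pass at 11.6% (control) and 37.6% (Penny). At a 30% share the arm rates are 0.7 × 65.5 + 0.3 × 11.6 = 49.3% and 0.7 × 86.4 + 0.3 × 37.6 = 71.8%, and Fisher power is 74.2%. It is 78.0% at a 5% share and 77.4% at 50%. Part of this fall reflects the lower overall pass rates, so adjustment would not recover all of it.

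**Step 7, what adjustment buys.** Patient-level logistic model, 72 per arm, 20% twice daily, log odds ratio 1.2 (65.5% vs 86.4% is ln 3.35 = 1.21), balanced arms.

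| gap in pass rate | SE, unadjusted → adjusted | z, unadjusted → adjusted |
|---|---|---|
| 15 points | 0.406 → 0.410 | 2.91 → 2.93 |
| 45 points | 0.372 → 0.412 | 2.74 → 2.91 |

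By Φ(z − 1.96), power stays at about 83% in the first row and goes from about 78% to 83% in the second.

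**The case against.** The strongest reply is that randomisation is individual and 1:1, so dosing frequency is balanced in expectation and the test's error rate already allows for chance imbalance. That stands. A reader might infer from the rule that the arm comparison is biased. The documents do not support that, because the rule applies equally in both arms.

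A reader might also take the Step 2 gaps, for instance a 4.5-point shift at p = 0.97 (0.10 × 45.0), as the size of the problem. Those figures need independent doses and identical patients, and at p = 0.97 once-daily patients pass at 89.2%, not the planned 65.5%. Step 3 is the fairer basis.

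A third tempting claim is that adjustment sharpens the estimate. In a logistic model it does not: the standard error of the log odds ratio rises slightly and the target becomes a conditional odds ratio. The gain is in power, and it is negligible unless the gap is large.

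The plan also has partial safeguards. Section 9.1 compares baseline clinical factors between arms and tests 80%, 90% and 100% cut-offs, and the gap shrinks at the lower ones. Section 9.1 can also be read as modelling the proportion of adherent days. On that reading, the SD 0, ρ = 0 gap is 95.4% vs 91.0% of days, and a 10-point imbalance moves the result by only 0.10 × 4.4 = 0.4 points. These points limit the size, but none of them accounts for dosing frequency in the 95% comparison.

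Finally, taking every dose on time is the behaviour being measured, so a harder regimen is a real burden and not an artefact. That is fair, and it is a reason to adjust for regimen rather than to change the outcome definition.

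**Conclusion.** The point holds as a minor improvement. Under the 8.3 rule, patients on more than one dose a day are less likely to reach 95% of days at the same per-dose behaviour, unless same-day doses are perfectly correlated. Nothing in 6.2 or 9.1 accounts for it. The consequence is exposure to chance imbalance and a modest loss of power.

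Anchored at 65.5% for once-daily patients, a 10-point imbalance is worth about 5 points in the extreme case and about 1 to 2.5 points once patients vary, against the 20.9-point target. Every figure rests on an assumed correlation and spread, and on a multi-dose share that the documents do not state. If that share is small, so is the effect.

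**What to change.** In 9.1, pre-specify baseline dosing frequency (once vs more than once daily, from the prescription at randomisation) as a fixed covariate in the primary model. Report the primary outcome by dosing frequency within each arm.

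Because the odds ratio then becomes conditional on dosing frequency, also report the risk difference standardised over dosing frequency. This keeps a result on the scale of the 20.9-point target.

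The cost is a few lines in the analysis plan and no new data. No regimen, adherence definition or study procedure changes. The downsides are the change in the meaning of the odds ratio and a small return if few patients take more than one dose a day.
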